### 10.4.3 SAMPLE SIZE

Approximately 500 participants will be enrolled to obtain 400 evaluable participants. The evaluable sample size is the same as the evaluable sample size used in “De Novo Classification Request for Cognivue”. The primary null and alternative hypotheses are:

$$H_0: \kappa \leq 0.40 \quad \text{vs.} \quad H_1: \kappa > 0.40$$

where  $\kappa$  is the quadratic weighted kappa statistic calculated from the above DCT-MMSE classification table. Power for quadratic weighted kappa requires assumptions of the values on the diagonal and off-diagonal of the table, which is a large number of assumptions. Power will thus be calculated for the unweighted kappa which requires fewer assumptions. It is assumed that the quadratic weighted kappa will be similar to or larger in magnitude than the unweighted kappa and with similar standard error as the unweighted kappa, so the study will be powered to show that the unweighted kappa  $> 0.4$  with the expectation it will then be sufficiently powered to show that the quadratic weighted kappa  $> 0.4$ . An evaluable sample size of 400 subjects yields at least 80% power to reject the above null hypothesis at one-sided 0.025 level of significance under the assumptions that: (1) the true kappa is 0.52 or more; (2) the marginal percentage of participants categorized as impaired is between 20% and 42.5% for DCTclock; (3) the marginal percentage of participants categorized as impaired for MMSE is the same as that for DCTclock; (4) the marginal percentage of participants categorized as unimpaired for DCTclock is the same as the marginal percentage of participants categorized as impaired for DCTclock; (5) the marginal percentage of participants categorized as unimpaired for MMSE is the same as that for DCTclock; and (6) the marginal percentage of participants categorized as indeterminate is between 15% and 60% for each of DCTclock and MMSE and is equivalent between DCTclock and MMSE.

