## 3 OBJECTIVES AND PURPOSE

The overall objective of this study is to demonstrate the safety and effectiveness of DCTclock as an adjunctive tool for use by clinicians to evaluate cognitive function in adults aged 55-95. There are four specific aims of the proposed project.

Aim 1: Examine the agreement between DCTclock classifications and a reference standard, the Mini-Mental State Exam (MMSE).

Aim 2: Determine the test/re-test reliability of DCTclock

Aim 3: Determine the construct validity of DCTclock via comparison with traditional paper and pencil neuropsychological tests.

Aim 4: Characterize the incidence of serious device related adverse events

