### 10.4 DESCRIPTION OF STATISTICAL METHODS

#### 10.4.1 GENERAL APPROACH

All subjects will undergo testing with DCTclock, MMSE, and MoCA. A non-inferiority analysis using a two-sided tests (TOST) approach will be conducted comparing the quadratic weighted kappa between DCTclock and MoCA to the quadratic weighted kappa between MMSE and MoCA.

The remaining analysis comparing DCTclock to MMSE will be descriptive, providing two-sided 95% confidence intervals of important parameters when necessary.

Descriptive statistics include sample size, mean, standard deviation, median and quartiles for continuous variables, and counts and percents for categorical variables. All confidence intervals will be two-sided 95% confidence intervals, and all p-values will be two-sided, using a two-sided 0.05 level of significance. There will be no imputation of missing data. Statistical analysis will be conducted with R version 3.4 or higher.

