#### 10.4.2 ANALYSIS OF THE PRIMARY EFFECTIVENESS ENDPOINT

The primary effectiveness analysis will be carried out using quadratic weighted kappa scores. A two-sided test (TOST) approach will be conducted, comparing the agreement between the MMSE and DCTclock scores with MoCA scores.

The kappa statistics will be calculated from the following table:

MoCA	
------	--

DCTclock/ MMSE		Impaired	Indeterminate/intermediate	Unimpaired	Total
	Impaired	a	b	c	a+b+c
	Indeterminate /intermediate	d	e	f	d+e+f
	Unimpaired	g	h	i	g+h+i
	Total	a+d+g	b+e+h	c+f+i	a+b+c+d+e+f+ g+h+i

This portion of the analysis will be carried out on the primary endpoint population and will only include scores from the first examination.

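### The 80% power belongs to a one-sample DCTclock–MMSE kappa test, while the primary analysis compares two kappas against MoCA

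*Protocol*

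**What the plan says.** Protocol 10.4.3 labels H0: kappa ≤ 0.40 against H1: kappa > 0.40 as primary. The kappa in question "is the quadratic weighted kappa statistic calculated from the above DCT-MMSE classification table". The sizing statement is that "An evaluable sample size of 400 subjects yields at least 80% power to reject the above null hypothesis", "at one-sided 0.025 level of significance", assuming "the true kappa is 0.52 or more". Every other assumption concerns the DCTclock and MMSE marginals; MoCA does not appear.

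Protocol 10.4.1 describes the formal analysis as non-inferiority by TOST, "comparing the quadratic weighted kappa between DCTclock and MoCA to the quadratic weighted kappa between MMSE and MoCA", and makes the remaining DCTclock-to-MMSE comparisons descriptive. Protocol 10.4.2, which is the primary analysis section, repeats this: a TOST "comparing the agreement between the MMSE and DCTclock scores with MoCA scores". The 3×3 tables in 10.2 and 10.4.2 have DCTclock or MMSE in the rows and MoCA in the columns.

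Aim 1 (section 3) and the primary endpoint (section 4.1.1 and the opening of section 10) describe agreement of DCTclock with MMSE. The opening of section 10 also states an aim of non-inferiority to MMSE.

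**The concern.** These are two different tests. One compares a single kappa with a fixed threshold, with MMSE as reference. The other is a difference between two dependent kappas that share MoCA as reference. They differ in estimand, null hypothesis, reference and standard error, so power for one does not carry over to the other. The table that 10.4.3 points back to does not appear before it.

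Two success criteria are on the page: DCTclock–MMSE kappa above 0.40, or DCTclock no worse than MMSE against MoCA. One can be met while the other fails, and the text does not rank them. In a pivotal study this leaves open which result counts as success, and whether 400 participants are enough for the analysis that will be run.

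**Working it through.** **1. The plan's own figure.** Inputs from 10.4.3: n = 400; true kappa 0.52 against null 0.40 (difference 0.12); one-sided alpha 0.025 (z = 1.96); impaired and unimpaired each 20% to 42.5%, with equal marginals for both tests. The calculation is for unweighted kappa, as the section says ("so the study will be powered to show that the unweighted kappa" exceeds 0.40). I used the large-sample (Fleiss–Cohen–Everitt) variance for a 3×3 table with marginals (p, 1−2p, p).

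Power = Φ((0.12 − 1.96·SE0)/SE1), where SE0 and SE1 are the standard errors under the null and the alternative. The protocol does not give the off-diagonal cells, so I took the largest SE over symmetric tables:

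| Impaired | SE1 | SE0 | Power |
|---|---|---|---|
| 20% | 0.0401 | 0.0425 | (0.12 − 0.0833)/0.0401 = 0.92 → 82% |
| 33.3% | 0.0350 | 0.0367 | (0.12 − 0.0719)/0.0350 = 1.37 → 92% |
| 42.5% | 0.0398 | 0.0431 | (0.12 − 0.0845)/0.0398 = 0.89 → 81% |

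Just outside the stated range, power drops below 80% (74% at 15% impaired, 79% at 45%). Using SE1 alone gives 85% to 93% at the same three points. The claim of at least 80% is reproduced for the hypothesis it was computed for. The enrolment figure also checks: 400/0.80 = 500.

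**2. The test in 10.4.1 and 10.4.2.** The parameter is Δ = κw(DCTclock, MoCA) − κw(MMSE, MoCA), with H0: Δ ≤ −margin. The protocol gives no margin, no kappa against MoCA and no correlation between the two kappas, so what follows rests on assumptions:

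- three latent normal ratings cut into three categories;
- 20%, 30% or 42.5% impaired, and the same unimpaired;
- both MoCA kappas equal, between 0.46 and 0.64;
- n = 400.

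Simulation puts the SE of the estimated Δ at about 0.035 to 0.054. With true Δ = 0 and one-sided alpha 0.025, power = Φ(margin/SE − 1.96):

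| Margin | SE 0.054 | SE 0.035 |
|---|---|---|
| 0.05 | 15% | 30% |
| 0.10 | 46% | 82% |
| 0.15 | 79% | 99% |
| 0.20 | 96% | >99% |

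The smallest margin with 80% power is (1.96 + 0.84) × SE, which is 0.10 to 0.15. If DCTclock is truly 0.05 lower, with SE 0.045 and margin 0.10, power is Φ((0.10 − 0.05)/0.045 − 1.96) = Φ(−0.85), about 20%.

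If TOST is meant as two-sided equivalence, power is lower. With equal kappas of about 0.51 to 0.54 it is roughly 12–67% at margin 0.10 and 77–99% at 0.15.

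**3. Can the two criteria disagree?** Same model, n = 400, 30% impaired and 30% unimpaired, weighted kappas throughout:

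| κ(DCTclock, MMSE) | κ(DCTclock, MoCA) | κ(MMSE, MoCA) | Passes kappa > 0.40 | Passes MoCA non-inferiority |
|---|---|---|---|---|
| 0.59 | 0.46 | 0.64 | about 100% | under 1% at margins up to 0.15; about 7% at 0.20 |
| 0.41 | 0.59 | 0.59 | about 4% | about 62% at 0.10; about 93% at 0.15 |

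So which section governs can decide the outcome.

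**The case against.** The best reply is that the DCTclock–MMSE kappa is the real primary test, so the power statement is correct and 10.4.1 and 10.4.2 are what went astray. There is support for this. Aim 1 and the endpoint text name agreement with MMSE. The evaluable set in 10.3 requires DCTclock and MMSE but not MoCA. Section 10.4.10 refers to the formal test of the weighted kappa in the singular. This stands as a reason not to assume that the MoCA comparison must govern. It does not remove the problem, because on that reading the primary analysis section and its tables describe the wrong test.

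A second reply is that 10.1 defers detail to a SAP, which was not available here and may state the margin. That is fair for the margin alone. It does not help with the contradiction, since the protocol itself attaches its primary hypotheses and power to one test and its primary analysis to another.

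Third, the power figures in step 2 rest on assumed margins, kappas and a latent-normal model, and they range from poor to ample. That is also fair: they show that power for the MoCA comparison is undetermined, not that it is inadequate.

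Finally, it would be too strong to say that no DCTclock–MMSE kappa is foreseen, since 10.4.3 presupposes one. The narrower statement holds: no such table is set out, 10.4.2 does not include that kappa, and the PPA and NPA in 10.4.4 are each computed against MoCA.

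**Conclusion.** The concern holds. The protocol states two incompatible primary tests, and its sample size and power belong to only one of them. That power is sound for its own hypothesis (about 81% to 93%, depending on marginals and variance formula). It is not a property of the analysis in 10.4.1 and 10.4.2. For that analysis, with equal true kappas and the assumptions above, 400 participants give 80% power only if the margin is about 0.10 to 0.15 or wider, and much less if DCTclock is slightly worse. The contradiction rests on the text alone; only the size of the power gap depends on the assumptions. It should be resolved before any outcome data are examined.

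**What to change.** Choose one primary hypothesis and state it identically in 10.2, 10.4.1, 10.4.2 and 10.4.3, and align the endpoint wording in 4.1.1 and section 10.

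- **If the MoCA-referenced comparison is primary:** write H0: κw(DCTclock, MoCA) − κw(MMSE, MoCA) ≤ −margin; state and justify the margin; say whether one-sided non-inferiority or two-sided equivalence is meant; and replace the 80% statement with the power that n = 400 gives for this paired contrast, showing the assumed kappas and their correlation. Make DCTclock–MMSE kappa > 0.40 a named secondary analysis with its own 3×3 table, so that Aim 1 is answered.
- **If DCTclock–MMSE kappa > 0.40 is primary:** put the DCTclock-by-MMSE table and that test in 10.4.2, and make the MoCA comparison secondary. The existing power statement can then stay.

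The cost is protocol wording and, on the first route, one power simulation. The correction itself adds no participants. On the first route the restated power may fall below 80% if a tight margin is chosen; the sponsor would then have to accept that figure or revisit the sample size.

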#### 10.4.10 SUB-GROUP ANALYSIS

All above effectiveness analyses (with the exception of the formal hypothesis test of the weighted kappa) may be repeated by (1) age (below median age, at or above median age); (2) sex; (3) education level; (4) language fluency test score (below median, at or above median) (5) medical history; and (6) current medications.

In addition, it is expected that the DCTclock test’s ability to identify impaired participants exceeds that of MMSE when participants are mildly impaired. Thus, for participants who score unimpaired on MMSE but impaired on DCTclock, scores on the neuropsychology battery test may be further inspected as follows to assess how often the DCTclock yielded the correct diagnosis in these cases. Specifically, the following will be presented on this subset of participants (when available):

- Percentage of participants scoring in the impaired range on the MoCA test (25 or below)
- Percentage of participants scoring 1.5 standard deviations below the mean on two or more of the following tests (Benton Judgement of Line, Rey Complex Figure, DKEFs, Digit Span, Blocks, Trails, Symbol Digit).
- Percentage of participants 2 standard deviations below the mean on one of the following tests (Benton Judgement of Line, Rey Complex Figure, DKEFs, Digit Span, Blocks, Trails, Symbol Digit).

---

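### The 80% power in Protocol 10.4.3 holds for the unweighted kappa; where both kappas equal 0.52, the quadratic weighted test has about 65–77%

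*Protocol*

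**What the plan says.** Protocol 10.4.3 tests a null kappa of at most 0.40, where kappa "is the quadratic weighted kappa statistic calculated from the above DCT-MMSE classification table". It declines to power that statistic because too many cell assumptions would be needed: "Power will thus be calculated for the unweighted kappa which requires fewer assumptions". The link between the two statistics is the assumption that the weighted kappa is "similar to or larger in magnitude than the unweighted kappa and with similar standard error as the unweighted kappa".

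The section then says that 400 evaluable participants "yields at least 80% power to reject the above null hypothesis at one-sided 0.025 level of significance". The null hypothesis referred to is the weighted one. The listed conditions are:

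- a true kappa of 0.52 or more;
- impaired shares between 20% and 42.5%;
- equal impaired and unimpaired shares within each test;
- the same margins for DCTclock and MMSE;
- an indeterminate share of 15% to 60%.

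None of these limits how often one test says impaired while the other says unimpaired.

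**The concern.** The standard error of a kappa is not a free assumption. It follows from the cell probabilities and the weights. Quadratic weights charge an impaired-versus-unimpaired disagreement four times as much as an adjacent one, so the weighted statistic depends heavily on a few cells. If its standard error is materially larger when the two kappas are equal, the similar-standard-error link fails exactly where the plan sets its minimum effect, and the stated power does not belong to the test named in the hypothesis. This is the only power statement in the protocol, and a reader would take 80% as assured at 0.52.

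**Working it through.** **Inputs (all from Protocol 10.4.3).** n = 400; one-sided 0.025 (z = 1.960); null 0.40; alternative 0.52; both tests with margins (p, 1−2p, p), p from 0.20 to 0.425.

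**Formulas.** Large-sample (Fleiss-Cohen-Everitt) variance:

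Var(κ) = { Σ p_ij [w_ij − (w̄_i. + w̄_.j)(1−κ)]² − [κ − p_e(1−κ)]² } / { n(1−p_e)² }

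Here w_ij = 1 on the diagonal and 0 elsewhere (unweighted), or w_ij = 1 − (i−j)²/4 (quadratic). Power = Φ(0.12/SE − 1.960). For 80% power the SE must not exceed 0.12/(1.960 + 0.842) = 0.0428.

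**Step 1: the plan's figure.** For the unweighted kappa at 0.52, the largest SE over all tables with these margins is 0.0401 (p = 0.20), below 0.0428. Using the largest SE under both null and alternative, power is 82.0% at p = 0.20, 89.9% at 0.30 and 81.3% at 0.425. At least 80% reproduces for the unweighted kappa.

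**Step 2: a table with both kappas at 0.52.** Take 52% perfect agreement and 48% chance agreement. At p = 0.20 each impaired/unimpaired cell is 0.48 × 0.2 × 0.2 = 0.0192 and each adjacent cell is 0.48 × 0.2 × 0.6 = 0.0576.

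- Unweighted: disagreement 2(0.0192) + 4(0.0576) = 0.2688; chance 0.56; κ = 1 − 0.2688/0.56 = 0.52.
- Quadratic: disagreement 2(0.0192) + 4(0.0576)/4 = 0.0960; chance 0.20; κ = 1 − 0.0960/0.20 = 0.52.

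SEs are 0.0387 and 0.0502. Asymptotic power is Φ(0.12/0.0387 − 1.960) ≈ 87% unweighted and Φ(0.12/0.0502 − 1.960) ≈ 67% weighted.

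**Step 3: across the stated range** (simulated power of the Wald test, 100,000 tables per row; ratios from unrounded SEs):

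| p | SE unweighted | SE weighted | Ratio | Power unweighted | Power weighted |
|---|---|---|---|---|---|
| 0.20 | 0.0387 | 0.0502 | 1.30 | 86% | 65% |
| 0.25 | 0.0364 | 0.0478 | 1.31 | 90% | 69% |
| 0.30 | 0.0352 | 0.0462 | 1.31 | 92% | 72% |
| 0.35 | 0.0350 | 0.0450 | 1.28 | 92% | 74% |
| 0.40 | 0.0359 | 0.0440 | 1.23 | 90% | 76% |
| 0.425 | 0.0368 | 0.0437 | 1.18 | 89% | 77% |

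Every weighted SE exceeds 0.0428. Asymptotic weighted power is 66.7% to 78.5%, or 62% to 74% if the null SE sets the critical value. The weighted SEs are not special to the chance-type table: with these margins and both kappas at 0.52, the smallest and largest weighted SE over all compatible tables coincide.

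**Step 4: how far the shortfall reaches.** Hold the unweighted kappa at 0.52 in symmetric tables and move disagreement from the impaired/unimpaired cells to the adjacent cells:

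| Impaired/unimpaired cells | Weighted kappa | Asymptotic power |
|---|---|---|
| at chance rate | 0.52 | 67–79% |
| 10% below chance | 0.534–0.551 | 79–95% |
| 25% below chance | 0.556–0.596 | 92–99.9% |
| none | 0.66–0.83 | near 100% |

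Asymptotically, 80% is reached at a weighted kappa of 0.536 (p = 0.20) down to 0.522 (p = 0.425). By simulation at p = 0.20 it takes about 0.54.

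**The case against.** The strongest reply is that the power claim is conditional. Similar standard error is a stated assumption, and tables with a weighted SE 18% to 31% larger fall outside it. That is fair as a reading of the text, but it does not rescue the figure. The section also allows the two kappas to be merely similar, and when they are equal under the stated margins the weighted SE is fixed at 0.0437 to 0.0502. The two halves of the assumption cannot both hold there.

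The second reply stands: the failing case is an edge. On an ordered scale with a middle category, disagreements are likely to be mainly adjacent, and Step 4 shows how quickly power recovers. A reader might infer that the trial is underpowered or needs more than 400 evaluable participants. The documents do not support that; they leave the disagreement pattern unspecified.

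A reader might also set the assumption that "the marginal percentage of participants categorized as impaired for MMSE is the same as that for DCTclock" against the expectation in 10.4.10 that DCTclock's "ability to identify impaired participants exceeds that of MMSE when participants are mildly impaired", and infer that power collapses under unequal margins. That does not follow. Section 10.4.10 speaks of mildly impaired participants and gives no difference in margins, so any gap would be the reader's own input and would break the plan's equal-margin conditions. A loss of power in the unweighted test would not carry over to the weighted test named in the hypothesis.

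Finally, 10.4.1 and 10.4.2 describe the primary analysis as a comparison of two weighted kappas against MoCA, and 10.4.1 makes the remaining DCTclock–MMSE analysis descriptive. That conflict is separate and comes first. It does not make the calculation in 10.4.3 right.

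**Conclusion.** The point holds in limited form. The 80% is correct for the unweighted kappa. It is not assured for the quadratic weighted test to which 10.4.3 attaches it: at a true value of 0.52 for both kappas, simulated power is about 65% to 77% over the stated margins. This rests on the plan's own n, alpha, null and equal margins, and on a Wald test with the standard large-sample variance.

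The shortfall is confined to the boundary and disappears once the weighted kappa exceeds the unweighted one by at most about 0.02. That threshold is itself conditional, and a weighted kappa of 0.54 should not be read as enough in general. At 20% margins with an unweighted kappa of 0.57, asymptotic power is about 61% at a weighted kappa of 0.52 and 78% at 0.54. The statement should be corrected; it is not a reason to change the size of the trial.

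**What to change.** 1. Reconcile 10.4.3 with 10.4.1 and 10.4.2: decide whether the primary test is the single DCTclock–MMSE kappa against 0.40 or the comparison of two kappas against MoCA, and state power for the weighted-kappa test that is kept.
2. If the single kappa is kept, delete the similar-standard-error link. Compute power directly for the quadratic weighted kappa over a small grid of 3×3 tables with the stated margins, running from chance-type to mostly adjacent disagreement, and state the assumed rate of impaired-versus-unimpaired disagreement. With symmetric tables of the kind used in Step 4, that rate is the only further input.
3. Restate the claim, for example: *With 400 evaluable participants, and provided the unweighted kappa is about 0.52 and does not exceed the weighted kappa, 80% power requires a true weighted kappa of about 0.54; at 0.52 power is about 65% to 77%, depending on the margins.*

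For the single-kappa test the cost is one recalculation and a reworded paragraph, with a somewhat less favourable stated figure. No extra participants are needed.

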### 10.4.4 SECONDARY AGREEMENT ANALYSIS

Agreement analysis: Additional agreement analyses between DCTclock and MMSE scores on detecting cognitive status will be carried out as follows:

- To better visualize the relationship between the two tests, the DCTclock and MMSE continuous scores will be plotted separately against the MoCA scores in a scatter plot, superimposed with a line of identity.
- Linear and rank linear regression analyses will be conducted and p-values with 95% CI will be calculated for the y-intercept and slope of each model. Either the Pearson (linear regression) or the Spearman (rank regression) correlation coefficients will be produced, and superimposed onto the scatter plots for each regression method, along with 95% confidence intervals and the estimated regression line.
- From Table I, the following statistics will be calculated for each of the tables (DCTclock vs MoCA and MMSE vs MoCA):

- Positive Percent Agreement (PPA) =  $a/(a+d+g)*100$  and its 95% Wilson CI
- Negative Percent Agreement (NPA) =  $(e+f+h+i)/(b+c+e+f+h+i)*100$  and its 95% Wilson CI.
- No formal hypotheses will be carried out on the PPA and NPA calculations, although 95% CIs will accompany them.

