#### 4.1.1 PRIMARY ENDPOINT

Primary endpoint: DCTclock and MMSE assessment of impaired, unimpaired or indeterminant/intermediate status. The primary analysis will assess agreement of DCTclock with the reference standard, MMSE, in identifying unimpaired and impaired test subjects.

---

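### Aim 1 and the Section 10.4.4 lead-in call for DCTclock–MMSE agreement, but every visit 1 agreement analysis laid out is against MoCA, and the one direct kappa, in 10.4.3, refers to a table the protocol does not contain

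*Protocol*

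**What the plan says.** - **Objective.** Section 3, Aim 1, is agreement between DCTclock classifications and MMSE as the reference standard. Section 4.1.1 repeats it for the primary endpoint: "The primary analysis will assess agreement of DCTclock with the reference standard, MMSE, in identifying unimpaired and impaired test subjects".
- **Lead-in of 10.4.4.** "Additional agreement analyses between DCTclock and MMSE scores on detecting cognitive status will be carried out as follows".
- **Analyses listed in 10.4.4.** In the first bullet, "the DCTclock and MMSE continuous scores will be plotted separately against the MoCA scores in a scatter plot". In the second, the correlations and fitted lines are "superimposed onto the scatter plots for each regression method, along with 95% confidence intervals and the estimated regression line", so they concern the same MoCA pairings. In the third, for PPA and NPA, "the following statistics will be calculated for each of the tables (DCTclock vs MoCA and MMSE vs MoCA").
- **Tables.** Sections 10.2 and 10.4.2 put DCTclock or MMSE in the rows and MoCA in the columns.
- **Primary method.** Section 10.4.1 compares the DCTclock–MoCA quadratic weighted kappa with the MMSE–MoCA one.
- **Sample size.** Section 10.4.3 tests H0: κ ≤ 0.40, where κ is a quadratic weighted kappa from a DCTclock–MMSE classification table said to stand above it. Its margin assumptions concern DCTclock and MMSE only.

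**The concern.** The objective is a direct comparison of two tests, but the analyses written out are two separate comparisons with a third test. If the analysis list is followed as it stands, the trial could report that DCTclock agrees with MoCA about as well as MMSE does, yet not say whether DCTclock and MMSE classify the same people the same way. Aim 1 would then have no prespecified result.

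The one place where a direct kappa appears, 10.4.3, does not close the gap. It refers to a table that is not there, and it conflicts with the primary method in 10.4.1 and 10.4.2.

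**Working it through.** **1. Which pair of tests does each analysis compare?**

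| Section | Pairing at visit 1 |
|---|---|
| 10.2, 10.4.2 tables | DCTclock or MMSE by MoCA |
| 10.4.1 primary method | DCTclock–MoCA kappa against MMSE–MoCA kappa |
| 10.4.4 plots, regressions, correlations | each test against MoCA |
| 10.4.4 PPA, NPA | each test against MoCA |
| 10.4.5 | none; each test against its own retest |
| 10.4.6 | DCTclock and MMSE each against the neuropsychological battery; correlations only |
| 10.4.10 | only participants unimpaired on MMSE and impaired on DCTclock; optional; no agreement statistic |
| 10.4.3 | DCTclock–MMSE kappa, from a table not shown |

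The schedule in 7.3.4 lists MMSE within the battery, so 10.4.6 could yield a DCTclock–MMSE correlation. A correlation of scores is not agreement of classifications.

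**2. The plan's own figure.** Inputs from 10.4.3: 400 evaluable participants, true unweighted kappa 0.52, null 0.40, one-sided 0.025, margins (p, 1-2p, p) with p from 20% to 42.5%. I used the large-sample variance of kappa, with disagreement spread in proportion to chance, and power = Φ(0.12/SE - 1.96).

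- p = 0.20: SE 0.0387; 0.12/0.0387 - 1.96 = 1.14; power 0.87
- p = 1/3: SE 0.0350; 0.12/0.0350 - 1.96 = 1.47; power 0.93
- p = 0.425: SE 0.0368; 0.12/0.0368 - 1.96 = 1.30; power 0.90

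The stated figure of at least 80% is reproduced. So the sample size belongs to a direct DCTclock–MMSE kappa, which neither 10.4.2 nor 10.4.4 computes.

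**3. Can the two MoCA kappas stand in for the direct one?** Assume that all three tests share the margins (p, 1-2p, p). Section 10.4.3 gives these for DCTclock and MMSE; extending them to MoCA is my assumption. Quadratic weights are 1 for the same category, 0.75 for adjacent categories and 0 for opposite ones. Then κ = (Po - Pe)/(1 - Pe), with Pe = 1 - p for these margins. I minimised and maximised the DCTclock–MMSE kappa by linear programming over all 27-cell DCTclock × MMSE × MoCA tables, with both MoCA kappas held fixed.

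| Both MoCA kappas | Direct kappa, p = 0.20 or 1/3 | Direct kappa, p = 0.425 |
|---|---|---|
| 0.50 | -0.50 to 1.00 | -0.18 to 1.00 |
| 0.52 | -0.44 to 1.00 | -0.14 to 1.00 |
| 0.60 | -0.20 to 1.00 | 0.02 to 1.00 |

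**4. One bound by hand** (p = 0.20, Pe = 0.80). This table attains the lower bound:

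| DCTclock | MMSE | MoCA | Share |
|---|---|---|---|
| Impaired | Unimpaired | Indeterminate | 20% |
| Indeterminate | Impaired | Impaired | 20% |
| Indeterminate | Indeterminate | Indeterminate | 40% |
| Unimpaired | Indeterminate | Unimpaired | 20% |

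Each test has margins 20/60/20.

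- DCTclock–MoCA: Po = 0.75×0.2 + 0.75×0.2 + 0.4 + 0.2 = 0.90; κ = 0.10/0.20 = 0.50
- MMSE–MoCA: Po = 0.75×0.2 + 0.2 + 0.4 + 0.75×0.2 = 0.90; κ = 0.50
- DCTclock–MMSE: Po = 0 + 0.75×0.2 + 0.4 + 0.75×0.2 = 0.70; κ = -0.10/0.20 = -0.50

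The upper bound of 1.00 is reached when DCTclock and MMSE give everyone the same category.

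**The case against.** The strongest objection is 10.4.3. It makes the DCTclock–MMSE weighted kappa the primary hypothesis parameter, and that hypothesis cannot be tested without estimating it. A reader might infer from 10.4.4 that the trial plans no direct estimate at all, or that the gap exists whichever hypothesis is primary. The protocol supports neither inference. If the conflict between 10.4.3 and 10.4.1/10.4.2 is settled in favour of 10.4.3, Aim 1 is answered by the primary result. What stands is that the table 10.4.3 relies on is missing and that no analysis section computes the kappa.

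The lead-in can also be read as comparing how well each test agrees with MoCA, in line with the non-inferiority aim at the start of Section 10. That is a fair reading of the lead-in, but it leaves Aim 1 and the primary endpoint unmatched. The first bullet also says it is meant to show how the two tests relate to each other, which two separate MoCA plots do not do.

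Section 10.1 leaves detail to a SAP, and 10.4.1 promises further descriptive comparison of DCTclock with MMSE. An extra descriptive table could well sit in the SAP. The point here is different: the protocol's own list of agreement analyses does not match its lead-in or its aim.

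Finally, the bounds are worst cases. A reader might infer that the direct kappa would probably fall below 0.40. That does not follow. Kappas of 0.50 with MoCA imply a direct kappa of about 0.29 to 0.31 only if DCTclock and MMSE are independent given MoCA's own underlying score. If the three tests were equally good measures of one trait, the direct kappa would also be 0.50.

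**Conclusion.** The point holds as an inconsistency between the stated aim and the listed analyses. No analysis section specifies a visit 1 DCTclock-by-MMSE table or an agreement statistic from it, and the single reference to one, in 10.4.3, leads to a table that is absent. The size of the gap is that two MoCA kappas of 0.50 leave the direct kappa undetermined between -0.50 and 1.00 (-0.18 and 1.00 at 42.5% impaired). Even two of 0.60 allow a direct kappa well below the null value of 0.40. These ranges assume equal margins for all three tests and describe what is possible, not what is likely. The point is tied to the choice of primary hypothesis and should be resolved together with it.

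**What to change.** - Add to the protocol the visit 1 DCTclock-by-MMSE 3x3 table on the Evaluable set, with its quadratic weighted kappa and 95% CI, percent agreement for each category with Wilson CIs, and the direct scatter plot and correlation. Name this as the Aim 1 output.
- Make the table reference in 10.4.3 point to it.
- State whether the primary test is this kappa (H0: κ ≤ 0.40) or the MoCA-based comparison in 10.4.1 and 10.4.2, so that the same kappa is not both the primary parameter and an unconnected secondary output.
- Reword the 10.4.4 lead-in so that its MoCA analyses are described as each test's agreement with MoCA. Those analyses can stay.

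The cost is protocol and SAP wording, one table with its statistics, and one plot. Both tests are already given at visit 1, so no new data are needed.
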